Version #: 6

Date Submitted: May 29, 2018

NCT03082391

Registry Based, Randomized Controlled Trial comparing Long-Term Results of Heavyweight

versus Medium Weight Mesh in Ventral Hernia Repair

P.I.: [name] FACS

Director, Cleveland Clinic Comprehensive Hernia Center

Version #: 6

Date Submitted: May 29, 2018

NCT03082391

INTRODUCTION

Approximately five million laparotomies are performed annually in the United States with upwards of 25% of these patients developing a ventral hernia postoperatively.¹ Despite the prevalence of ventral hernias, the surgical approach to these procedures lacks standardization. In fact, nearly 20%-50% of patients undergoing ventral hernia repair (VHR) will experience a hernia recurrence.²

There are several factors that can contribute to ventral hernia recurrence. One of these is the use of prosthetic reinforcement. Although previous studies have shown that the use of mesh during VHR significantly decreases the risk of ventral hernia recurrence, guidelines for the ideal prosthetic material remain unknown. In terms of synthetic mesh, there are proponents that argue the value of medium weight material (40-60 g/m²) in order to combat the risk of postoperative deep surgical site infection and minimize the risk of a “stiff abdomen” or chronic pain syndromes.³⁻⁵ On the other hand, however, proponents of a heavier weight material (> 80 g/m²) argue that its tensile strength leads to a long-term, durable hernia repair with decreased risk of hernia recurrence.³⁻⁵

To help determine if mesh weight has an impact on postoperative pain, we propose a registry-based, randomized clinical trial (RCT) through the Americas Hernia Society Quality Collaborative (AHSQC). The AHSQC is a multicenter, nationwide quality improvement effort with a mission to improve value in hernia care.⁶ Data are collected prospectively in the routine care of hernia patients for quality improvement purposes. The information collected in the AHSQC offers a natural repository of information that can be used for research, in addition to its quality improvement purpose. We hypothesize that patients who undergo ventral hernia repair with medium weight mesh will have significantly less pain than those patients who undergo ventral hernia repair using heavyweight mesh one year after operation. Both the intended randomization arms of the study are accepted standard of care practices in use by surgeons.

Version #: 6

Date Submitted: May 29, 2018

NCT03082391

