Specific Aim #1: To determine if the use of a medium weight material leads to a decrease in pain intensity at one year following ventral hernia repair.

Specific Aim #2: To determine if there is a difference in ventral hernia recurrence at one year following surgery.

Specific Aim #3: To determine if there is a difference in the rate of deep surgical site infection at 30-days following surgery between the two mesh types.

Specific Aim #4: To determine if there is a difference in the quality of life between the two groups at one year following surgery.

STUDY DESIGN

This trial will be the first registry-based prospective study performed in the hernia disease space. Registry-based trials use the data available in a pre-existing database to increase the efficiency of performing RCTs.⁷ To date, few high-quality RCTs have been performed evaluating treatments for hernia disease due to the high cost and logistical challenges associated with operationalizing this type of research. In our case, the AHSQC will serve as our platform. The exposure variables (mesh type) and outcomes of interest (pain intensity, quality of life, recurrence, and deep surgical site infection) for this trial are already captured within the AHSQC database, which will allow for long-term follow-up and data capture with minimal additional effort outside that of routine care.⁷

There will be a total of four sites participating in this study, including the Cleveland Clinic Foundation, Vanderbilt University Medical Center, Medical College of Wisconsin, and Greenville Health System. Specific patient inclusion criteria include patients aged 18 years or older, presenting for an elective, single-stage, open, retromuscular reconstruction of a clean (CDC wound class 1) midline abdominal wall defect, are able to achieve midline fascial closure, have a hernia defect

Version #: 6

Date Submitted: May 29, 2018

NCT03082391

width \leq 20 centimeters measured intraoperatively, are able to tolerate general anesthesia, and are able to give informed consent. Patients will be excluded from our analysis if they undergo laparoscopic or robotic repair of an abdominal wall defect, have CDC wound class 2, 3, or 4, are unable to undergo successful retromuscular mesh placement, are pregnant, or are unable to give informed consent.

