Patients will be randomized to heavyweight (> 75 gm/m²) versus medium weight (40-60 gm/m²) mesh at the time of operation. Specifically, patients will be randomized precisely at the point of mesh placement during the operation. All currently available polypropylene meshes and their densities have been confirmed by their respective manufacturer as follows:

AHSQC #	Frequency Used	Mesh Name	Type	Density (g/m ²)	Source
88	1.8	ULTRAPRO Mesh (Ethicon Inc.)	PP	28	Ethicon
118	0.1	VitaMESH Blue (Atrium Medical Corp.)	PP	29	Atrium
5	14.7	Bard Soft Mesh (Bard/Davol Inc.)	PP	43	Bard
70	1.9	PROLENE Soft Mesh (Ethicon Inc.)	PP	45	Ethicon
123	1.4	Parietene (Covidien)	PP	46	Covidien
72	0.6	ProLite Ultra Mesh (Atrium Medical Corp.)	PP	50	Atrium
116	4	VitaMESH (Atrium Medical Corp.)	PP	50	Atrium
125	0.2	Freedom Octomesh (Insightra Medical)	PP	55	Insightra Medical (http://studiorwebgroup.ca/liaison/files/5614/0741/6221/Insightra_Freedom.pdf)
69	0.8	PROLENE Mesh	PP	76	Ethicon
71	0.6	ProLite Mesh (Atrium Medical Corp.)	PP	85	Atrium
4	2.5	Bard Mesh (Bard/Davol Inc.)	PP	105	Bard

Yellow = Lightweight Mesh; Blue = Medium Weight Mesh; Red = Heavy Weight Mesh

Baseline patient demographics will be obtained at initial patient recruitment. Standard baseline AHSQC questionnaires will be completed following patient recruitment for baseline comparison. Operative details will be collected and stored in the AHSQC database. Patient follow-up visits will occur at 4 weeks (\pm 2 weeks) and 12 months (\pm 2 months) postoperatively. Follow-up

Version #: 6

Date Submitted: May 29, 2018

NCT03082391

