at 4 weeks (± 2 weeks) and 12 months (± 2 months) will occur either in person or using Cleveland Clinic platform for virtual visits. In the instances where a subject cannot attend to their 1-year follow-up visit in person or through a virtual visit, information will be collected through a telephone contact. Pain intensity at different time points will be assessed using the NIH PROMIS Pain Intensity 3A scale, which is collected for all patients entered into the AHSQC. Patient quality of life and functional mobility will be assessed using the Hernia Quality of Life (HerQLes), which is also collected as standard for all patients entered into the AHSQC. Patients will be required to complete these forms at each clinic visit to allow for monitoring of postoperative progression and overall effect of heavyweight versus medium weight mesh on patient quality of life. Hernia recurrence will be assessed using the Ventral Hernia Recurrence Inventory, a validated questionnaire that can be performed either in person or via email or phone correspondence.⁸ At the time of the one month and one-year follow-up clinic visits, a routine physical examination will be performed on all patients. Confirmation of a recurrent hernia will occur if the patient reports recurrence of a bulge or hernia at the site of previous repair during the Ventral Hernia Recurrence Inventory questionnaire. If the surgeon's physical examination does not correlate with the patient-report hernia recurrence, an ultrasound or computed tomography scan will be ordered based on the usual practice of the surgeon. At the completion of the study protocol, patients will be informed as to the type of mesh that was used during the surgical operation. An additional question ("Do you feel your mesh?") will be asked to the subjects during the 1-year follow-up contact and this information will be stored in REDCap.

OUTCOMES TO BE INVESTIGATED

Each outcome to be investigated is based on the specific aims of the study and are listed below:

Version #: 6

Date Submitted: May 29, 2018

NCT03082391

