Specific Aim #1: To determine if the use of a medium weight material leads to a decrease in pain intensity at one year following surgery. This will be assessed with the use of the NIH PROMIS 3a Pain Scale. The change in scaled score one year after operation will be calculated by comparison to the scaled score obtained at baseline for each patient. The mean change at one year will be compared for each group (heavyweight mesh and medium weight mesh).

Specific Aim #2: To determine if there is a difference in ventral hernia recurrence at one year following surgery. Hernia recurrence will be determined using the Ventral Hernia Recurrence Inventory, a validated questionnaire using patient-reported outcomes to determine hernia recurrence after repair.⁸

Specific Aim #3: To determine if there is a difference in the rate of deep surgical site infection at 30-days following surgery between the two mesh types. Definitions of wound events are per the Centers for Disease Control and were agreed upon by all participating surgeons. These wound outcomes will be recorded in the AHSQC database at 30 days as follows:

Deep Incisional SSI

A **deep incisional SSI** must meet the following criteria:

Infection occurs within 30 days after the operative procedure AND the infection involves deep soft tissues (e.g., fascial and muscle layers) of the incision AND patient has at least ONE of the following:

- a. purulent drainage from the deep incision but not from the organ/space component of the surgical site

Version #: 6

Date Submitted: May 29, 2018

NCT03082391

- b. a deep incision spontaneously dehisces or is deliberately opened by a surgeon AND is culture-positive or not cultured AND the patient has at least one of the following signs or symptoms: fever ($>38^{\circ}\text{C}$), or localized pain, or tenderness. A culture-negative finding does not meet this criterion.
- c. an abscess or other evidence of infection involving the deep incision is found on direct examination, during invasive procedure, or by histopathologic examination or imaging test.
- d. diagnosis of a deep incisional SSI by a surgeon or attending physician.

NOTE:

- a. Classify an infection that involves both superficial and deep incision sites as a deep incisional SSI.
- b. Classify infection that involves superficial incisional, deep incisional, and organ/space sites as deep incisional SSI. This is considered a complication of the incision.

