The primary outcome measure of this study is the change in NIH PROMIS Pain Intensity Scale 3a scaled score one year after operation. The mean scaled score change at one year will be compared for each group (heavy weight mesh versus medium weight mesh). Patient reported outcomes within the AHSQC were evaluated for patients undergoing ventral hernia repair from July 2013 through August 2016. Twenty-three patients met criteria for medium weight mesh as defined in Table 1 and six patients meeting criteria for heavy weight mesh. Scaled score changes at one year after operation are summarized as below:

	Size	Mean	SD	Min	Lower Quartile	Median	Upper Quartile	Max
Medium weight (Group 1)	23	-10.3	10.9	30.7	41.9	46.3	53.3	71.8
Heavy weight (Group 2)	6	-7.5	6.3	30.7	41.7	47.8	53.2	54.5

Version #: 6

Date Submitted: May 29, 2018

NCT03082391

Using a two sample t-test allowing for unequal variance with equal sample sizes (1:1) group allocation of medium weight and heavyweight mesh, 160 patients per group will achieve a target power of 80% given an alpha of 0.05. Assuming a 10% loss to follow up at 1 year, a total of 352 patients will be recruited for this study (176 patients in each group).

STATISTICAL ANALYSIS

Categorical variables will be examined using Pearson's Chi-Square and all continuous variables will be examined using the non-parametric Wilcoxon signed rank test. The categorical variables will be reported using proportions and continuous variables will be reported using the median and the interquartile range.

Specific Aim 1: The Wilcoxon signed rank test will be performed to determine if the change from baseline to one-year follow-up is statistically significantly different between the medium weight and heavyweight mesh groups.

Specific Aim 2: The proportion of patients in each group reporting a hernia recurrence will be examined using Pearson's Chi-Square test to determine if there is a difference between the groups.

Specific Aim 3: The counts of the surgical site infections will be compared using Pearson's Chi-Square test to determine if an association exists between either type of mesh and frequency of SSI.

Specific Aim 4: The change in the HerQLes will be examined using the Wilcoxon signed rank test to determine if there is a difference in the quality of life after hernia repair for patients receiving medium weight vs heavyweight mesh.

Version #: 6

Date Submitted: May 29, 2018

NCT03082391

DATA SAFETY MONITORING BOARD

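### Does an early visit that may fall before day 30 leave the 30-day deep infection outcome (Aim 3) unascertained?

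*Combined protocol and SAP*

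**What the plan says.** STUDY DESIGN fixes two follow-up points: "Patient follow-up visits will occur at 4 weeks", with a margin of two weeks either way, and 12 months. It adds that follow-up "at 4 weeks (± 2 weeks) and 12 months (± 2 months) will occur either in person" or by virtual visit. The same section later refers to the early visit as the one at one month. It assigns the pain and quality-of-life forms and a physical examination to the clinic visits. A telephone fallback is given for the one-year contact only.

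Aim 3 is "To determine if there is a difference in the rate of deep surgical site infection at 30-days following surgery between the two mesh types". Under OUTCOMES TO BE INVESTIGATED, the case definition opens with "Infection occurs within 30 days after the operative procedure AND the infection involves deep soft tissues" and then lists the qualifying findings. The same paragraph says "These wound outcomes will be recorded in the AHSQC database at 30 days as follows".

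On the source of the data, the INTRODUCTION says of the registry: "Data are collected prospectively in the routine care of hernia patients for quality improvement purposes". STUDY DESIGN lists deep SSI among the outcomes the registry already holds and gives as a reason for the design "data capture with minimal additional effort outside that of routine care". STATISTICAL ANALYSIS, Specific Aim 3, says "The counts of the surgical site infections will be compared" by Pearson's chi-square test.

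**The concern.** The outcome runs to day 30, but the one scheduled early contact can take place as early as day 14, and even its target date is two days short. If a site filled in the infection field from that visit and did not return to it, an infection that appeared between the visit and day 30 could be entered as no event. The protocol describes no day-30 call, chart review or completion rule for such patients, and the Aim 3 analysis does not say how to treat someone whose observation stopped before day 30. With four sites, practice could differ.

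The stake would be an undercount of deep infections, and so less information on Aim 3. Infection risk is one of the arguments the INTRODUCTION gives for medium weight mesh, so the aim is not a trivial one.

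**Working it through.** The protocol states no figure to reproduce here. The check is calendar arithmetic, followed by a comparison of the relevant passages.

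**Inputs.** Early visit at 4 weeks with a 2-week margin (STUDY DESIGN); onset window and recording time of 30 days (OUTCOMES TO BE INVESTIGATED, Specific Aim #3).

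**Visit window.**
- Target: 4 × 7 = day 28.
- Limits: 28 − 14 = day 14 and 28 + 14 = day 42.
- Permitted days: 42 − 14 + 1 = 29.
- Before day 30: days 14 to 29, which is 29 − 14 + 1 = 16 days.
- On or after day 30: 42 − 30 + 1 = 13 days.

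**Part of the 30-day period that follows the visit.**
- Visit on day 28: 30 − 28 = 2 days, 2/30 = 6.7% of the period.
- Visit on day 14: 30 − 14 = 16 days, 16/30 = 53% of the period.
- Visit on day 30 or later: none.

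These are shares of time, not of infections. Turning them into missed events would need the timing of onset, the spread of actual visit dates and the proportion of later infections that reach the registry through routine care. The documents give none of these, so no event figure is offered. If routine care captures every later infection, the number missed is zero whatever the visit date.

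**Passages side by side.**
1. The visit text assigns pain and quality-of-life forms and a physical examination to the visit. It does not assign infection recording to it.
2. The Aim 3 text has its own rule: record in the registry at 30 days, counting onset within 30 days. It does not mention the visit.
3. The registry text says deep SSI is already captured there, from routine care.
4. Several of the qualifying findings can arise away from a trial visit: an abscess found on imaging or at an invasive procedure, or a diagnosis made by a surgeon or attending physician.

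The visit window therefore limits infection ascertainment only if the visit is assumed to be the source, and the protocol does not say that. The visit schedule and the day-30 record can both be followed without conflict.

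**Effect on the comparison if some late events were missed.** Let the true risks be p1 and p2, let a share m of events be missed in each arm, and suppose there are no false positives. The observed ratio is p1(1 − m) / [p2(1 − m)] = p1/p2, which is unchanged. The observed difference is (1 − m)(p1 − p2), which is smaller. The cost is some attenuation of the absolute difference and some precision, not a spurious difference between the arms.

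**The analysis line.** It refers to surgical site infections without the word deep or a time limit. The aim it sits under supplies both, so an analyst would count deep SSI within 30 days.

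**The case for a change.** The strongest reply is that the recording rule says when and where status is entered, not how it is learned for a patient last seen on day 14, 21 or 28. Two sites could both believe they had complied, one entering no infection on the strength of a day-14 visit and the other checking the chart on day 30. The telephone fallback does not help, since it covers the one-year contact alone.

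As a reading of the text, this stands: the procedure is not written down. It does not establish a defect. A site that carries forward a day-14 status has not recorded the outcome at 30 days as the rule requires, so the undercount comes from departing from the plan. How the registry completes its 30-day entry belongs to the registry's procedures, which are not part of these documents, and silence here does not show that no procedure exists.

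The equal share m in both arms is an assumption. The same visit window applies to both arms, and patients learn their mesh type only at the end of the study, which supports it. The operating surgeon places the mesh and so knows it, which means the documents do not prove it. A chart check would not remove that knowledge. It could also miss infections treated elsewhere, and it would add work in a design chosen to avoid it.

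**Conclusion.** No change follows. The protocol already calls for deep SSI with onset within 30 days to be recorded in the registry at 30 days, in both arms. The early visit may precede day 30, by 2 days at its target date and by up to 16 at the edge of its window, but it is not named as the source of the infection data. The unstated step is an operating detail that sites and analysts can fill sensibly. A sentence citing the registry's day-30 procedure would be a courtesy to the reader, not a correction.

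This rests on two assumptions: that sites follow the stated day-30 recording rule, and that any late infection that is missed is missed about equally in the two arms. The documents show no failure of either. The number of events at risk is unknown. Aim 3 is a secondary aim with no stated power. The primary outcome is the one-year change in pain score, and the target of 352 patients was derived from that score alone, so neither depends on this point.

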The allocation of the patient to either a heavyweight or medium weight mesh will be performed in the operating room based on final CDC wound classification after the posterior components are reapproximated. Randomization will be performed according to a computer-generated block randomization scheme at each participating institution. The corresponding prosthetic material will then be placed with at least 5 cm of fascial coverage on all sides of the defect. The mesh will be fixed with mechanical sutures. Drains will be placed above the mesh, when utilized, and the timing of removal will be based on the surgeon's standard practice. Skin must be closed with either suture or staples. Fascial closure and management of the wound dressings will occur based on the surgeon's standard practice.

ANTICIPATED TIME FRAME

Version #: 6

Date Submitted: May 29, 2018

NCT03082391

Estimated patient accrual time is one year with data collection to occur over one year from the last enrolled patient. Data analysis and manuscript production will occur within six months of completion of data collection.

PATIENT RISKS AND DISCOMFORTS

As with any surgical procedure, there are some associated risks and they will be discussed in a separate surgical consent form. The subjects may experience some pain, bleeding and discomfort; however this is with any surgical operation. Common occurrences following hernia repair include seroma or hematoma around the hernia repair, inflammation, opening of the wound, or infection. Subjects may also experience additional therapies or treatments, including the removal of the mesh to treat any of these events.

PATIENT BENEFITS

There are no direct benefits to subjects for participating in this study. Subject participation will help us better understand the long-term outcomes of heavyweight and mediumweight mesh with respect to patient quality of life and hernia recurrence.

COSTS TO THE SUBJECTS

There are no extra costs to the subjects associated with the research. Procedures related to the preoperative evaluation and the hernia surgery are considered standard of care and will be the responsibility of the subject and the subject's insurance company.

Version #: 6

Date Submitted: May 29, 2018

NCT03082391

ALTERNATIVES TO PARTICIPATION

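### Aims 1 and 4 use the baseline score only by subtraction and ignore the site within which randomisation is blocked; adjusting for both can gain precision at no extra data cost.

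*Combined protocol and SAP*

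**What the plan says.** Under Outcomes to be Investigated, Specific Aim #1, the protocol says that "The change in scaled score one year after operation will be calculated by comparison to the scaled score obtained at baseline for each patient" and that "The mean change at one year will be compared for each group". The Statistical Analysis section, Specific Aim 1, compares the mesh groups as follows: "The Wilcoxon signed rank test will be performed to determine if the change from baseline to one-year follow-up is statistically significantly different". For Aim 4, "The change in the HerQLes will be examined using the Wilcoxon signed rank test". Neither aim names a covariate, a regression model or a stratification factor, and nothing elsewhere in the document supplies one.

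On allocation, the Surgical Procedure section says: "Randomization will be performed according to a computer-generated block randomization scheme at each participating institution". The Study Design section names four institutions. The same section shows that the baseline data will be in hand: "Pain intensity at different time points will be assessed using the NIH PROMIS Pain Intensity 3A scale, which is collected for all patients" in the registry, and quality of life is measured with "the Hernia Quality of Life (HerQLes), which is also collected as standard for all patients entered into the AHSQC". Baseline questionnaires are completed after recruitment.

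The Power Calculation section sizes the trial on the unadjusted change score and states that "160 patients per group will achieve a target power of 80% given an alpha of 0.05".

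**The concern.** A change score is a baseline adjustment with the slope fixed at 1. If the true regression slope of the one-year score on the baseline score is below 1, which is usual for a noisy patient-reported scale, subtraction over-corrects and adds baseline noise to the outcome. Estimating the slope removes that noise. In large samples with 1:1 allocation it cannot do worse than fixing the slope.

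Two things are at stake. First, the primary confidence interval may be wider than the collected data allow, in a trial with no power reserve. Second, if the arms happen to differ in baseline pain, the change-score estimate in that realised trial is pulled off centre whenever the slope is not 1. A decision to adjust taken only after seeing such an imbalance would be post hoc.

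Leaving out site is a smaller matter. Blocking within site balances the arms across sites, so a test that ignores site can only be mildly conservative. It carries no false-positive risk.

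**Working it through.** **Inputs from the Power Calculation section.** Mean change −10.3 (SD 10.9, n = 23) for medium weight and −7.5 (SD 6.3, n = 6) for heavyweight mesh, so the difference is 2.8 points. The test is a two-sample t-test allowing unequal variances, alpha 0.05, 160 per group, 176 recruited per group, 10% loss.

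**The plan's own figure.** Two-sided Welch power at 160 per arm: SE = √((10.9² + 6.3²)/160) = 0.995, power 80.0%. The stated figure reproduces. With 10% loss from 176, 176 × 0.9 = 158.4, so about 158 per arm remain. Then SE = 1.002, power is 79.5%, and the 95% CI half-width is 1.97 points.

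**Effect of estimating the baseline slope.** Let ρ be the correlation between baseline and one-year score, and k the baseline SD divided by the one-year SD. The variance of the adjusted estimate relative to the change-score estimate is

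(1 − ρ²) / (1 + k² − 2ρk).

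The documents give neither ρ nor k, so both are assumed over a range. Power is the Welch power at an effective n of 158 divided by the ratio.

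| k | ρ | Variance ratio | Power at 158 per arm |
|---|---|---|---|
| 1.0 | 0.3 / 0.5 / 0.7 | 0.65 / 0.75 / 0.85 | 93.3 / 89.6 / 85.6% |
| 0.8 | 0.3 / 0.5 / 0.7 | 0.78 / 0.89 / 0.98 | 88.2 / 83.9 / 80.3% |
| 1.2 | 0.3 / 0.5 / 0.7 | 0.53 / 0.61 / 0.67 | 97.0 / 94.8 / 92.6% |
| equal to ρ | any | 1.00 | 79.5% (no gain) |

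Example for k = 1, ρ = 0.5: (1 − 0.25)/(1 + 1 − 1) = 0.75, and 158/0.75 = 211 effective per arm. With k = 1 the CI half-width falls from 1.97 to 1.97 × √0.65 = 1.59 points at ρ = 0.3, and to 1.97 × √0.85 = 1.82 points at ρ = 0.7.

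**Simulation check.** With 158 per arm, four sites, normal data, a pooled change SD of √((10.9² + 6.3²)/2) = 8.90 and robust (HC3) standard errors, power was 79–81% for Welch on change and 77–79% for a between-group rank-sum test on change. The model with baseline and site gave 94%, 89% and 85% at k = 1 for ρ = 0.3, 0.5 and 0.7; 82% at ρ = 0.7, k = 0.8; and 79% at ρ = 0.7, k = 0.7. With the unequal pilot SDs of 10.9 and 6.3, at ρ = 0.5 and k = 1, the result was 89% adjusted against 79% for Welch.

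**Chance baseline imbalance.** The change-score estimate shifts by ρ/k − 1 points per point of imbalance. At k = 1 that is −0.7 at ρ = 0.3 and −0.3 at ρ = 0.7. The baseline SD implied by a change SD of 8.90 is 8.90/√(2(1 − ρ)), or 7.52 and 11.49. One SE of the baseline difference is that SD × √(2/158), or 0.85 and 1.29 points. The shift for a one-SE imbalance is therefore 0.7 × 0.85 = 0.59 or 0.3 × 1.29 = 0.39 points, which is 21% or 14% of the 2.8-point effect.

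**Site.** No site variance is given. At an assumed 1%, 2% or 5% share of the variance, Welch power at 158/(1 − share) is 79.9%, 80.3% or 81.5%. The type I error of a test that ignores site is 2(1 − Φ(1.96/√(1 − share))) = 4.9%, 4.8% or 4.4%.

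**Aim 4.** No HerQLes SD is given. The variance ratio is scale-free, so the same percentages apply under the same assumed ρ and k.

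**The case against.** The strongest reply is that nothing in the plan fails. Change from baseline is a legitimate prespecified outcome, the trial was sized on it, and the sizing reproduces. The benefit of adjustment depends on two quantities that the documents do not give: it is 2% of variance at ρ = 0.7, k = 0.8, and zero when k equals ρ. The site term is worth little on any plausible assumption. HerQLes may also have a different correlation and SD ratio from PROMIS 3a. All of this stands, and it limits the point to efficiency.

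A second reply is that the fix is more than an added covariate. The Wilcoxon test named in the Statistical Analysis section cannot take covariates, so a linear model would replace the named primary test, and that section reports continuous variables as medians and interquartile ranges. This also stands and should be disclosed. It does not defeat the proposal, because the Outcomes and Power Calculation sections both define the comparison as one of mean change, and that is what the linear model estimates. The Welch test was used as the benchmark here because the sizing rests on it; a between-group rank-sum test does slightly worse in the simulation.

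What does not stand is that the uncertain size is a reason to leave things as they are. Large-sample precision is not lost in any case examined, and the price is four degrees of freedom out of about 320.

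**Conclusion.** The concern holds as a recommendation about precision. Baseline enters Aims 1 and 4 only by subtraction, site enters nowhere, and both are already recorded. At 158 evaluable patients per arm, power for 2.8 points would move from 79.5% to about 86–93% if baseline and one-year SDs are equal and ρ is 0.3–0.7, or to 80–88% if the baseline SD is 0.8 of the one-year SD, with no gain in the limiting case. Almost all of this comes from baseline. These figures rest on the pilot SDs, one of them from six patients, and on assumed values of ρ and k. The planned comparison of change is neither biased nor anti-conservative on this account.

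**What to change.** For Aim 1, prespecify a linear model of the one-year PROMIS 3a score on mesh arm, baseline PROMIS 3a score and site, with heteroscedasticity-robust standard errors because the pilot SDs differ. Report the adjusted mean difference with its 95% CI. With baseline in the model, the arm coefficient targets the same mean difference in change that the Outcomes and Power Calculation sections describe. Use the same model for HerQLes with its own baseline score. Keep an unadjusted two-sample comparison of change as a sensitivity analysis, and state plainly that the model replaces the named test as primary.

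The cost is analysis-plan wording, fixed before anyone sees unblinded outcome data. No variable, visit or patient is added, and sample size and conduct do not change.

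### The 80% power is for an unequal-variance t-test on mean change, but Aim 1 is to be analysed with a Wilcoxon test, to which that figure does not apply

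*Combined protocol and SAP*

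**What the plan says.** **Sizing.** The Power Calculation section names the change in PROMIS Pain Intensity 3a score at one year as the primary outcome and says that its mean will be compared between arms. The method is given as "Using a two sample t-test allowing for unequal variance with equal sample sizes (1:1) group allocation", with the result that "160 patients per group will achieve a target power of 80% given an alpha of 0.05". The inputs are registry figures: mean change -10.3 (SD 10.9) in 23 medium weight patients and -7.5 (SD 6.3) in 6 heavyweight patients.

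**Outcome.** Under Outcomes to be Investigated, Specific Aim #1 agrees with this: "The mean change at one year will be compared for each group".

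**Analysis.** The Statistical Analysis section takes a different route: "all continuous variables will be examined using the non-parametric Wilcoxon" test, and "continuous variables will be reported using the median and the interquartile range". The entry for Specific Aim 1 repeats the Wilcoxon test for the between-group comparison of change. No t-test, mean difference or confidence interval appears in that section.

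**The concern.** The test that justified 352 patients is not the test that will produce the primary result. Two things follow.

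- **The power statement.** It describes a test that the analysis section does not run, and no power is given for the one that it does run.
- **The quantity.** The trial was sized on a 2.8-point difference in mean change. A rank test with medians and interquartile ranges does not address that quantity when the arms have different spreads, as the plan's own SDs imply. Without the mean difference and its interval, neither a null nor a positive result can be read against the planning target.

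The plan calls the test a signed rank test, which is a paired or one-sample procedure. It is read here as the two-sample rank-sum test, the only reading that compares two independent arms. The name is a separate point, and correcting it alone would leave this mismatch in place.

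**Working it through.** **Inputs (Power Calculation section).** Difference in mean change = -7.5 - (-10.3) = 2.8, which is derived because the plan does not print it. SDs 10.9 and 6.3; alpha 0.05; 1:1 allocation. Sidedness is not stated. Two-sided is inferred because it reproduces 160 per group, whereas one-sided needs only 125.

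**Step 1: the plan's own figure.** Unequal-variance t-test, n = 160 per group:

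- SE = sqrt((10.9² + 6.3²)/160) = sqrt(158.50/160) = 0.9953
- noncentrality = 2.8/0.9953 = 2.813; Satterthwaite df = 254.6
- power from the noncentral t = **80.03%**

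At 159 per group the power is 79.8%, so 160 is the smallest size that reaches 80%. The stated figure is reproduced exactly, for this test.

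**Step 2: the rank-sum test, if changes are normal.**

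- P(medium weight change < heavyweight change) = Φ(2.8/sqrt(10.9² + 6.3²)) = Φ(0.2224) = 0.588
- null SE of that proportion = sqrt(321/(12 × 160 × 160)) = 0.0323
- (0.588 - 0.5)/0.0323 = 2.72; power ≈ P(Z > 1.96 - 2.72) ≈ 0.78

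With the exact variance of the rank statistic under these normal distributions, the result is 77.6%. Simulations of 60,000 trials give 77.6% to 77.8%. Under normality, 80% would need about 170 to 172 evaluable patients per group.

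**Step 3: other shapes, same means and SDs, 160 per group (simulation).**

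| Shape of change | Rank-sum | Unequal-variance t-test |
|---|---|---|
| Uniform | 63% | 80% |
| Normal | 78% | 80% |
| t, 10 df | 82% | 80% |
| t, 5 df | 88% | 80% |
| Laplace | 93% | 80% |

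The t-test stays near 80% throughout, because means and SDs largely fix its power at this size. They do not fix the power of the rank test.

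**Step 4: can the documents settle the shape?** No. The minimum, quartile and maximum columns of the table run from 30.7 to 71.8. They cannot describe changes that average -10.3 and -7.5, and they look like raw scores.

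**Step 5: equal means, unequal spread.** With no mean difference, normal changes and SDs 10.9 and 6.3, the rank-sum test rejects in about 5.6% of simulated trials, against about 5.0% for the unequal-variance t-test. The rank-sum test is therefore not a clean test of mean change here.

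**The case against.** **The loss of power is not established.** A reader might infer that the primary test simply has 77 to 78% power and that the trial is underpowered. The documents do not support that. The figure needs normality, which the plan never states, and tails only slightly heavier than normal (t with 10 df) already put the rank-sum test above 80%. This objection stands, and the conclusion is worded accordingly.

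**The gap under normality is small beside the inputs.** The means are printed to one decimal, so the difference lies between about 2.7 and 2.9. At 2.7 the t-test itself has 77.1% power. The heavyweight SD rests on 6 patients. Sizing with a t-test and analysing with ranks is also common practice. All this is fair and limits the severity. It does not answer the mismatch in the quantity being compared.

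**The mean comparison is promised elsewhere.** A reader might infer that the mean difference will never be reported. That goes too far, because both the outcome section and the power section say that mean change will be compared. What can be said is that the analysis section specifies no test, estimate or interval for it.

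**The misnamed test is the larger defect.** That may be so, but once it is renamed the power statement still belongs to a different test.

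**Conclusion.** The point holds as a mismatch between sizing and analysis, and that part needs no distributional assumption. The stated 80% is correct for the unequal-variance t-test and says little about the planned Wilcoxon test.

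Read as rank-sum, two-sided, with the plan's means and SDs, the planned test has about 78% power if changes are normal, and about 63% to 93% over the other shapes tried. Whether the protocol overstates or understates the power therefore depends on a distribution that it does not give. The sample size was not miscalculated, and nothing here calls for a larger one. The main consequence is for interpretation: the 2.8-point mean difference on which the trial was planned has no specified test or interval in the analysis section. Severity is minor to moderate.

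**What to change.** Make the sizing and the primary analysis agree, without adding patients.

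1. **Preferred.** Make the unequal-variance comparison of mean change the primary Aim 1 analysis, reported as a mean difference with its 95% CI. Keep the two-sample rank-sum test as a sensitivity analysis. The stated 80% at 160 evaluable patients per group then applies.
2. **If the rank-sum test stays primary.** Restate its power as about 78% at 160 per group, assuming normally distributed changes (difference 2.8, SDs 10.9 and 6.3). Show the range for other shapes, and still report the mean difference with its 95% CI beside the medians.

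The cost is a change of wording in one or two sections and, at most, one extra estimate with its interval. Option 1 gives up some resistance to outlying scores, which the sensitivity analysis partly covers. Option 2 puts a slightly less favourable and openly conditional power figure in the protocol.
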